10.5.3.4 Other safety data

Other safety data collected will be listed and summarized using descriptive statistics as appropriate. Notable values may be flagged. Notable/Abnormal values for safety data will be further specified in the RAP and will be used for shift tables.

Analyses will be performed on the safety set.

ECG

[figure not shown]
- shift table baseline to worst on-treatment result.
- listing of ECG evaluations for all patients with at least one abnormality.

[figure not shown]
Vital signs

- shift table baseline to worst on-treatment result
- table with descriptive statistics at baseline and change from baseline to worst post-baseline time points.

10.5.3.5 Tolerability

[figure not shown]
Tolerability will be summarized in terms of dose reductions or drug interruption due to an AE.

10.8 Interim analysis

An interim analysis will be performed after the first 30 patients enrolled have completed at least 16 weeks (4 cycles) of treatment with LDK378 or have discontinued earlier. The interim analysis will focus on full pharmacokinetics profile, safety and preliminary efficacy, including but not limited to:

- Pharmacokinetics: PK analysis will be performed. Plasma concentration of LDK378, and PK parameters for patients with extensive PK assessment will be summarized and listed.
- Safety: all adverse events observed by the data cutoff date will be summarized and listed. Separate summaries will be provided for SAE and death, respectively. Abnormal results on laboratory assessment and ECG will be presented and listed in detail.
- Efficacy: ORR observed by the data cutoff date will be estimated with corresponding binomial exact 95% CI.

[figure not shown]
Details of the analysis will be defined in RAP.

The primary clinical study report (CSR) will be produced after all patients have undergone at least 24 weeks (6 cycles) of treatment with LDK378 or have discontinued earlier. All available data from all patients up to this cutoff date will be analyzed. The additional data for any patients continuing to receive study treatment, as allowed by the protocol, will be further summarized in a report once these patients completed the study (addendum of the clinical study report).

10.9 Sample size calculation

Overall approximately 100 patients will be enrolled. This sample size was deemed to be adequate to assess safety, and tolerability and demonstrate the anti-tumor activity of LDK378 in Chinese patients.

The first 15 patients being enrolled in the phase I component will have a 5-day PK run-in period so to obtain approximately 12 evaluable PK profiles.

10.10 Power for analysis of key secondary variables

The study is not powered for formal hypothesis testing. However, with a total of 100 patients, if the observed ORR (key secondary endpoint) is 45% (45 responders in 100 treated patients), this will result in an exact binomial 90% CI of - [36.5% ,53.7%].

[figure not shown]
11 Ethical considerations and administrative procedures

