Data analysis	Using the PAS, PK concentration versus time profiles of LDK378 will be summarized separately for patients with extensive PK assessment and patients with sparse PK sampling. The mean and individual concentration versus time profiles of LDK378 will be displayed graphically for full PK profile and trough collections. LDK378 PK parameters, including but not limited to AUClast, AUC0-24h, AUCinf, Cmax, Tmax, Lambda z, terminal T1/2, T1/2,acc, Racc, CL/F (or CLss/F at steady state) and Vz/F, as appropriate will be derived from PK run-in patients with extensive PK assessment. All PK parameters will be summarized. The PK parameters and concentration data will be listed Safety data including adverse events, vital signs, ECG and laboratory abnormalities will be summarized and listed. For efficacy, ORR as assessed by investigator will be estimated and the binomial exact 95% CI provided. DOR will be listed by patient and described using Kaplan-Meier methods and relevant statistics. DCR will be estimated and the binomial exact 95% CI provided. PFS, and OS will be described using Kaplan-Meier methods and appropriate summary statistics. Efficacy data will be listed. [REDACTED] [REDACTED] [REDACTED]
Key words	ALK, NSCLC, LDK378

Amendment 3

Amendment rationale

As of 29-Sep-2015, of 103 patients treated, 66 patients have been discontinued from treatment and 37 are still receiving study treatment.

The amendment provides follow up evaluations for hepatic toxicities and work-up guidelines for potential Drug Induced Liver Injury (DILI) cases in order to optimize patient safety.

Other change was implemented in this amendment: Dose guidance modification for QTc text is being updated to provide clarification on monitoring procedure.

Changes to the protocol

Changes to specific sections of the protocol are shown in the track changes version of the protocol using strike through red font for deletions and red underlined for insertions.

The following sections to the protocol were changed:

- List of abbreviations updated with commonly used abbreviations
- Table 6-3: “Refer to Section 6.2.4.2 for additional follow-up” was added for AST or ALT and concurrent Total bilirubin management. Follow-up description updated for Grade 3 QTc interval prolonged.
- Section 6.2.4.2: Updated on following up evaluations for hepatic toxicities and work-up guidelines for potential Drug Induced Liver Injury (DILI) cases to align with Novartis Oncology trial standard language.

IRB/IEC

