1.3 Risk and Benefits

Overall benefit-risk

Ceritinib dosed at 750 mg once daily has remarkable anti-tumor activity and induces a high rate of rapid and durable responses and prolonged PFS in patients with advanced, ALK-positive NSCLC, regardless of whether they had been previously treated with an ALK inhibitor or were ALK inhibitor naïve. The substantial anti-tumor activity and resulting clinical benefit combined with the clinically manageable safety profile of ceritinib strongly support a positive benefit/risk balance for ALK-positive NSCLC patients.

Efficacy

Patients with prior ALK inhibitor treatment: ALK-positive NSCLC patients previously treated with crizotinib who have progressed and patients intolerant to crizotinib have no effective treatment options, have a dismal prognosis, and represent a population with a high unmet medical need. In ALK-positive NSCLC patients failing treatment with crizotinib, independent from the resistance mechanism involved, ALK translocation is still present and is still the oncogenic driver in almost all of the cases. Chemotherapy is not expected to provide a meaningful clinical benefit in these patients, as was recently demonstrated in a Phase III study (PROFILE 1007) of crizotinib vs. chemotherapy in the second-line setting ([Shaw et al 2013](#)).

In ALK-positive NSCLC patients previously treated with an ALK inhibitor and multiple prior lines of anti-neoplastic therapy, based on an independent review of tumor assessments, as of 31-Oct-2013, the response rate was 45.1% (95% CI: 37.1 - 53.3) and the median DOR was 7.1 months (95% CI: 5.6 – NE). The median PFS was 6.7 months (95% CI: 5.5 - 7.7) in Study [CLDK378X2101]. The median PFS is similar (overlapping 95% CIs) to that reported for crizotinib in the second-line setting (7.7 months (95% CI: 6.0 - 8.8)) and similar or better than that reported for chemotherapy (4.2 months (95% CI: 2.8 - 5.7) with pemetrexed and 2.6 months (95% CI: 1.6 - 4.0) with docetaxel) in the PROFILE 1007 study ([Shaw et al 2013](#)) for patients with locally advanced or metastatic ALK-positive NSCLC who had received prior treatment with one platinum-containing chemotherapy regimen. Therefore, ceritinib fulfills an existing unmet medical need.

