10.5.1.2 Analysis for key secondary objective

The analysis of ORR will be performed on the FAS. The ORR will be estimated and the 95% confidence interval (CI) based on the exact binomial distribution will be provided.

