3.4 Power for analysis of key secondary variables

With a total of 100 patients, if the observed ORR (key secondary endpoint) is 45% (45 responders in 100 treated patients), this will results in an exact binomial 90% CI of [36.5%, 53.7%].

4 Appendix 16.1.9 of CSR- Documentation of statistical method

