4.2.5 Confidence intervals

ORR/DCR/OIRR will be summarized in terms of percentage rates with 95% CIs. An exact binomial confidence interval (implemented using SAS procedure FREQ with EXACT statement for one-way tables) will be calculated ([Clopper & Pearson, 1934](#)).

SAS procedure FREQ will be used to estimate the proportion of responders (binary outcome = 1 or “Yes”), along with the associated 95% two-sided Pearson-Clopper CI. These estimates are obtained as follows:

```
PROC FREQ DATA = dataset;  
    TABLE binary event /  
        binomial(p = null proportion Level = “Yes”)  
        alpha = 0.05;  
    EXACT binomial;  
  
RUN;
```

When there are no responders, SAS does not produce a CI by default. To obtain a CI in this situation, PROC FREQ is used as specified above except changing **level**=”No”. From the results of this modified procedure, the values in percent of the LCL and UCL of a 0% response rate are calculated as follows:

$$\text{LCL}_{\text{LEVEL}=\text{”Yes”}} (\%) = 100\% - \text{UCL}_{\text{LEVEL}=\text{”No”}} (\%)$$

$$\text{UCL}_{\text{LEVEL}=\text{”Yes”}} (\%) = 100\% - \text{LCL}_{\text{LEVEL}=\text{”No”}} (\%)$$

[REDACTED]

[figure not shown]
[REDACTED]

[REDACTED]

[REDACTED]

[REDACTED]

[REDACTED]

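### Does the 90% interval that illustrates ORR precision conflict with the 95% interval planned for every ORR analysis?

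*Protocol*

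**What the plan says.** Protocol 10.10 first says that the study has no power calculation for a formal test. It then takes 45 responders among 100 treated patients as an example and states that "this will result in an exact binomial 90% CI of" 36.5% to 53.7%. SAP 3.4 gives the same example with the same level and limits.

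The analysis sections use a different level:

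- Protocol summary, data analysis: "ORR as assessed by investigator will be estimated and the binomial exact 95% CI provided".
- Protocol 10.5.1.2, key secondary analysis: "The ORR will be estimated and the 95% confidence interval (CI) based on the exact binomial distribution will be provided". SAP 3.2.10.1 says the same.
- Protocol 10.8, interim analysis: "ORR observed by the data cutoff date will be estimated with corresponding binomial exact 95% CI". SAP 3.2.12 says the same.
- SAP 4.2.5, programming rule: "ORR/DCR/OIRR will be summarized in terms of percentage rates with 95% CIs", with code that sets alpha to 0.05 and asks for the Clopper-Pearson interval.

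On sample size, protocol 10.9 and SAP 3.3 say only that about 100 patients was judged sufficient for safety, tolerability and anti-tumor activity. Neither states a target width or a minimum response rate.

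**The concern.** A precision statement normally uses the level at which the result will be reported. Here the only quantitative support for about 100 patients is a 90% interval, while all planned ORR intervals are at 95%. The ORR intervals quoted in protocol 1.2.1.2.2, 1.3 and 2.1 are also at 95%. A reader who misses the label would expect a tighter estimate than the study report will show.

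There is also a tempting comparison. Protocol 1.3 reports for an earlier study that "the response rate was 45.1% (95% CI: 37.1 - 53.3" in patients with a prior ALK inhibitor. That looks almost the same as 36.5% to 53.7%, but the two intervals are at different levels.

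If the 90% interval fed a success criterion or the choice of sample size, the lower level would be a real weakening. It could also be that the figure is a mislabelled 95% interval or a calculation error. Both possibilities need checking.

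**Working it through.** **Inputs.** Responders x = 45 and patients n = 100 (protocol 10.10). Level 90% (protocol 10.10, SAP 3.4) or 95% (protocol 10.5.1.2, SAP 4.2.5).

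**Formula.** Two-sided Clopper-Pearson interval with error alpha:

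- lower limit = alpha/2 quantile of Beta(x, n − x + 1) = Beta(45, 56)
- upper limit = 1 − alpha/2 quantile of Beta(x + 1, n − x) = Beta(46, 55)

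**Step 1: reproduce the printed figure (alpha = 0.10).** The limits are 36.52% and 53.71%, which round to the printed 36.5% and 53.7%. Tail check: P(X ≥ 45 | p = 0.365) = 0.0496 and P(X ≤ 45 | p = 0.537) = 0.0502, so about 5% in each tail. A Wald 90% interval (36.8% to 53.2%) and a Wilson 90% interval (37.1% to 53.2%) do not match. The figure is a true exact 90% interval, neither mislabelled nor miscalculated.

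**Step 2: same data at the reporting level (alpha = 0.05).** The limits are 35.03% and 55.27%.

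**Step 3: difference.**

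| Level | Interval | Width (points) |
|---|---|---|
| 90% | 36.52% to 53.71% | 17.19 |
| 95% | 35.03% to 55.27% | 20.24 |

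The ratio of widths is 20.24 / 17.19 = 1.18. The lower limit moves by 36.52 − 35.03 = 1.49 points and the upper by 55.27 − 53.71 = 1.56 points.

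**Step 4: what depends on the 90% interval?**

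- *Sample size:* protocol 10.9 and SAP 3.3 do not derive it from any interval.
- *Test or threshold:* none. Protocol 10.10 rules out formal testing, and no response rate is set for a limit to exceed.
- *Reported interval:* set at 95% in the analysis sections and in the SAP 4.2.5 code.
- *Interim analysis:* reports ORR at 95%, with no decision rule tied to it.

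Nothing in the visible text uses the 90% interval after it is stated.

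**Step 5: the earlier-study comparison.** The interval in protocol 1.3 is 53.3 − 37.1 = 16.2 points wide at 95%, against 20.2 points for 45/100. At nearly the same rate, that points to a larger sample. It also comes from independent review, while the key secondary ORR here is assessed by the investigator. The earlier study's investigator-assessed rate for these patients is 54.6% (46.6% to 62.4%), under RECIST 1.0 (protocol Table 1-2), whereas this study uses RECIST 1.1. Aligning the confidence levels would not make the two like for like, and neither protocol 10.10 nor SAP 3.4 invites the comparison.

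**The case for a change.** The best case for an edit is that it is cheap and would make the precision statement match what is reported. SAP section 3 is written as a draft of the study report's methods section, so the 90% sentence may end up beside 95% results. SAP 3.4 also keeps the word power in its heading but drops the protocol's remark that no formal test is planned, so the sentence stands there without context. A 90% level can be a legitimate planning choice, but one would expect a reason.

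The mismatch and the missing explanation stand. The Amendment 1 log entries for protocol 10.9 and 10.10 are blacked out, so a reason in superseded text cannot be excluded, but the current visible text has none.

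The need for a change does not stand. The level is printed in both places, so the report's reader is not misled. The report will carry the 95% interval for the observed data, which replaces any planning example. Recruitment was complete, with 103 patients treated, before the current protocol version, so the example can no longer inform enrolment. Editing only the SAP would also separate two sections that now agree, while SAP 4.1.1 records no differences from the protocol.

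**Conclusion.** The inconsistency is real but editorial. The printed 90% interval is correct and labelled. The planned 95% interval for the same 45/100 is about 3 points wider (20.24 − 17.19 = 3.05), with the lower limit about 1.5 points lower. The two statements answer different questions, one about a hypothetical result and one about what will be reported, and both can be true.

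No change to the plan follows, because there is nothing to gain in the analysis. The sample size, the estimate, the reported interval and any conclusion about response are the same either way. This rests on two points in the visible text: no test or response threshold is set, and the number of patients is not derived from an interval width. If either were otherwise, the choice of level would matter.

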11.1 Regulatory and ethical compliance

This clinical study was designed, shall be implemented and reported in accordance with the ICH Harmonized Tripartite Guidelines for Good Clinical Practice, with applicable local regulations (including European Directive 2001/20/EC and US Code of Federal Regulations Title 21), and with the ethical principles laid down in the Declaration of Helsinki.

11.2 Responsibilities of the investigator and IRB/IEC/REB

The protocol and the proposed informed consent form must be reviewed and approved by a properly constituted Institutional Review Board/Independent Ethics Committee/Research Ethics Board (IRB/IEC/REB) before study start. Prior to study start, the investigator is

required to sign a protocol signature page confirming his/her agreement to conduct the study in accordance with these documents and all of the instructions and procedures found in this protocol and to give access to all relevant data and records to Novartis monitors, auditors, Novartis Clinical Quality Assurance representatives, designated agents of Novartis, IRBs/IECs/REBs and regulatory authorities as required.

[figure not shown]
11.3 Informed consent procedures

Eligible patients may only be included in the study after providing written (witnessed, where required by law or regulation), IRB/IEC/REB-approved informed consent.

Informed consent must be obtained before conducting any study-specific procedures (i.e. all of the procedures described in the protocol). The process of obtaining informed consent should be documented in the patient source documents. The date when a subject's Informed Consent was actually obtained will be captured in their CRFs.

Novartis will provide to investigators, in a separate document, a proposed informed consent form (ICF) that is considered appropriate for this study and complies with the ICH GCP guideline and regulatory requirements. Any changes to this ICF suggested by the investigator must be agreed to by Novartis before submission to the IRB/IEC/REB, and a copy of the approved version must be provided to the Novartis monitor after IRB/IEC/REB approval.

Women of child bearing potential should be informed that taking the study medication may involve unknown risks to the fetus if pregnancy were to occur during the study and agree that in order to participate in the study they must adhere to the contraception requirement for the duration of the study. If there is any question that the patient will not reliably comply, they should not be entered in the study.

[figure not shown]
A large rectangular area of the page is completely blacked out, indicating that the original content has been redacted.

11.4 Discontinuation of the study

Novartis reserves the right to discontinue this study under the conditions specified in the clinical study agreement. Specific conditions for terminating the study are outlined in [Section 4.4](#).

11.5 Publication of study protocol and results

Novartis assures that the key design elements of this protocol will be posted in a publicly accessible database such as clinicaltrials.gov. In addition, upon study completion and finalization of the study report the results of this study will be either submitted for publication and/or posted in a publicly accessible database of clinical study results.

A series of horizontal lines of varying lengths are completely blacked out, indicating that the original content has been redacted.

11.6 Study documentation, record keeping and retention of documents

Each participating site will maintain appropriate medical and research records for this trial, in compliance with Section 4.9 of the ICH E6 GCP, and regulatory and institutional requirements for the protection of confidentiality of subjects. As part of participating in a Novartis-sponsored study, each site will permit authorized representatives of the sponsor(s) and regulatory agencies to examine (and when required by applicable law, to copy) clinical records for the purposes of quality assurance reviews, audits and evaluation of the study safety and progress.

Source data are all information, original records of clinical findings, observations, or other activities in a clinical trial necessary for the reconstruction and evaluation of the trial. Examples of these original documents and data records include, but are not limited to, hospital records, clinical and office charts, laboratory notes, memoranda, subjects' diaries or evaluation checklists, pharmacy dispensing records, recorded data from automated instruments, copies or transcriptions certified after verification as being accurate and complete, microfiches, photographic negatives, microfilm or magnetic media, x-rays, and subject files and records kept at the pharmacy, at the laboratories, and medico-technical departments involved in the clinical trial.

[figure not shown]
Data collection is the responsibility of the clinical trial staff at the site under the supervision of the site Principal Investigator. The study case report form (CRF) is the primary data collection instrument for the study. The investigator should ensure the accuracy, completeness, legibility, and timeliness of the data reported in the CRFs and all other required reports. Data reported on the CRF, that are derived from source documents, should be consistent with the source documents or the discrepancies should be explained. All data requested on the CRF must be recorded. Any missing data must be explained. Any change or correction to a paper CRF should be dated, initialed, and explained (if necessary) and should not obscure the original entry. For electronic CRFs an audit trail will be maintained by the system. The investigator should retain records of the changes and corrections to paper CRFs.

The investigator/institution should maintain the trial documents as specified in Essential Documents for the Conduct of a Clinical Trial (ICH E6 Section 8) and as required by applicable regulations and/or guidelines. The investigator/institution should take measures to prevent accidental or premature destruction of these documents.

Essential documents (written and electronic) should be retained for a period of not less than fifteen (15) years from the completion of the Clinical Trial unless Sponsor provides written permission to dispose of them or, requires their retention for an additional period of time because of applicable laws, regulations and/or guidelines.

11.7 Confidentiality of study documents and patient records

The investigator must ensure anonymity of the patients; patients must not be identified by names in any documents submitted to Novartis. Signed informed consent forms and patient enrollment log must be kept strictly confidential to enable patient identification at the site.

11.8 Audits and inspections

Source data/documents must be available to inspections by Novartis or designee or Health Authorities.

11.9 Financial disclosures

[figure not shown]
Financial disclosures should be provided by study personnel who are directly involved in the treatment or evaluation of patients at the site - prior to study start.

12 Protocol adherence

Investigators ascertain they will apply due diligence to avoid protocol deviations. Under no circumstances should the investigator contact Novartis or its agents, if any, monitoring the study to request approval of a protocol deviation, as no authorized deviations are permitted. If the investigator feels a protocol deviation would improve the conduct of the study this must be considered a protocol amendment, and unless such an amendment is agreed upon by Novartis and approved by the IRB/IEC/REB it cannot be implemented. All significant protocol deviations will be recorded and reported in the CSR.

